- ERP should be scheduled along the needs and requirements of the site EEG lab performing the ERP task – make sure to have a mutual calendar you can access for the purpose of scheduling appointments.

- ERP visits can be scheduled for 1 hour blocks in green include:
 - SENSE Theatre, id number, and age/sex of participant.
- **Immediately confirm with site EEG team of the scheduled date. Reserve parking**
- **SENSE Calendar:** include ERP, subject id, time, parking spaces reserved.

CASS (30 minutes)

- **Before scheduling CASS** visits you must:
 - (1) Establish with any groups that share research space the times for which you will be using the facilities.
 - (2) Figure out research helper availability, so you may know which research helpers are available when.
 - Do these two things BEFORE scheduling participants!
- **Confirm Research Helpers:** After scheduling a participant, contact available research helpers to confirm their availability.
- **Confirm Research Space:** Then email any groups sharing the research to let them know the date and time you will be using the CASS. Email lab members as needed to schedule space for CASS at the beginning of each week while study is active.
- **Reserve parking** for research helpers AND subject.
- Add CASS visit to **site lab calendar**, including subject id, location, time, research helpers, and reserved parking spaces.

SURVEY KIT

Send to parents before their assessment visit/have parents complete during visit:

- Cover Letter: instructions for questionnaire packet and appointment reminder
- Teacher letter: instructions of teacher questionnaires with deadline.
- Consent & Assent
 - Tell parents to read, but not sign
 - Come with questions
 - We will review and sign at visit
- Photo/Video Release.
- Collect information needed for NDAR
- Directions to the site location, including where to meet
- Medications Checklist
- Short Sensory Profile (SSP)
- Social Communication Questionnaire—Lifetime (SCQ-L)
- ABAS (Parent and Teacher)
- Child Behavior Checklist (CBCL)
- Social Responsiveness Scale-2 (SRS-2, Parent and Teacher)
- Parenting Stress Index Short Form (PSI)
- BRIEF 2
- Conners 3
- MASC-2 Parent Report

- Pubertal Development Scale (PDS)
- Gender Development Survey Parent Report (GDS-Parent)
- Quality of Play Questionnaire (QPQ)

(Parent Surveys: remind them **not** to fill in child's name, DOB, and other identifying information)

Visit 1 (Pre-Test) Only:

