Investigating Social Competence in Youth with Autism: A Multisite
RCT

Statistical Analysis Plan (SAP)

NCT03368001

Document Date: November 1, 2017

Document Source: Analytic Plan from MH114906

3.C.12. ANALYTIC PLAN: Aims and Hypotheses (Hyp)

Handling missing data, Full information maximum likelihood (FIML) estimation methods will be used.

Specific Aim 1: Show Efficacy of SENSE via Target Engagement of Memory for Faces

Hyp 1.1: Youth in the EXP group will demonstrate significantly faster growth in memory for faces (MFD and IMF) than youth in the ACC group. EXP youth will also have higher levels of memory for faces at follow-up.

Hyp 2.1: Youth in the EXP group will demonstrate significantly faster growth in social behavior (SRS and CASS) than youth in the ACC group. EXP youth will also have higher levels of prosocial behavior at follow-up.

Statistical Analysis: To address the above-mentioned hypothesis, we will use a 2-level multilevel growth model with treatment (EXP vs. ACC) predicting random intercepts and random linear slopes. The levels are (1) time of testing in months from study entry and (2) participant. Time will be centered at follow-up to enable interpreting the intercept as an end-point estimate. We will test EXP vs. ACC differences on means of the linear slope of time in order to test for differential change over time. We will also test EXP vs. ACC differences in follow-up-centered intercepts. A linear model is a reasonable model of social growth for such a short period (i.e., three months) with people who have a social impairment. The random intercept and slope accommodate dependency of time (pre, post, follow-up) within participant. Dependency of participants within cohort will be corrected for using design-robust standard errors (following procedures in Sterba¹²⁶). Site effects are not anticipated but will be examined by including 2 dummy covariates for site as predictors of intercepts and slopes; if not significant, these covariates will be removed. This model will be run in Mplus¹²⁷ general multilevel and structural equation modeling software capable of fitting both the univariate multilevel models for Specific Aim 1 and the multivariate multilevel models for Specific Aim 2, below.

Specific Aim 2: Linking Degree of Target Engagement and Mechanism-Based Functional Outcomes

Hyp 2.2. Growth in memory for faces (NEPSY, ERP) will mediate the effect of treatment on growth in social behavior (SRS, CASS).

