Statistical Analysis: To address Hyp 2.2, we will use a multivariate multilevel growth model (involving a linear growth model for memory and another linear growth model for social behavior). We will specify a mediation pathway at the participant-level from treatment (x) to the slope of memory for faces (m) to the slope of social behavior (y). The indirect effect will be tested using the 95% confidence interval around the product of the unstandardized coefficients for the (x→m) and (m→y) paths of the multilevel mediation model following procedures of Lachowicz, Sterba, and Preacher¹²⁸. The confidence interval will be estimated using the Monte-Carlo procedure described in Preacher and Selig,¹²⁹. Exclusion of zero will be interpreted as a significant indirect effect.

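### The SAP analyses SRS growth over three waves, but the protocol names the SRS-2 only in its baseline survey kit

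*SAP*

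**What the plan says.** **SAP, section 3.C.12.** Hyp 2.1 reads: "Youth in the EXP group will demonstrate significantly faster growth in social behavior (SRS and CASS) than youth in the ACC group". The growth model that serves this hypothesis uses three occasions: "The random intercept and slope accommodate dependency of time (pre, post, follow-up) within participant". It fixes the origin of time at the last one: "Time will be centered at follow-up to enable interpreting the intercept as an end-point estimate". Two contrasts are tested, the difference in mean slope and an end-point difference: "We will also test EXP vs. ACC differences in follow-up-centered intercepts". Hyp 2.2 adds a mediation claim, "Growth in memory for faces (NEPSY, ERP) will mediate the effect of treatment on growth in social behavior (SRS, CASS", in which the path runs from treatment "to the slope of memory for faces (m) to the slope of social behavior (y".

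**Protocol.** The only mention of the instrument is in the Survey Kit: "Social Responsiveness Scale-2 (SRS-2, Parent and Teacher". That kit is sent before, or completed during, the assessment visit. It also holds the consent and assent forms, with the instruction "Tell parents to read, but not sign", because signing takes place at that visit. Separate form lists are given under Post-Assessment and under Follow-Up (Forms). Neither names the SRS or SRS-2.

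**The concern.** A treatment difference in growth needs the outcome measured after baseline in both arms. Site staff work from the protocol's visit lists. If they do so literally, the SRS-2 is collected once, before treatment. One of the two named social-behaviour outcomes of Hyp 2.1, and the SRS mediation path of Hyp 2.2, would then have no data on change. The CASS does not replace it: the CASS is coded from a staged conversation, while the SRS-2 is rated by a parent or teacher. In a multisite trial there is a second risk, that some sites add the form on their own initiative and others do not.

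**Working it through.** **1. Comparison of the lists.**

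| Rating scale | Survey Kit | Post | Follow-up |
|---|---|---|---|
| ABAS, PDS, SSP, CBCL, BRIEF-2, GDS-Parent, PSI, Conners 3, MASC-2 Parent, QPQ | yes (10) | yes (10) | yes (10) |
| SCQ-Lifetime | yes | no | no |
| SRS-2 | yes | no | no |

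The count is 12 at baseline, 10 at post and 10 at follow-up; 12 − 10 = 2 are dropped. The SCQ-Lifetime is not a SAP outcome; the SRS-2 is. The match is by name: the later lists give the ABAS-3 without an informant.

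**2. The other SAP outcomes.** NEPSY Memory for Faces, ERP and CASS each appear at pre, post and follow-up. Among the SAP outcomes, the gap is specific to the SRS.

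**3. What can be estimated from baseline alone.** Let z be treatment (0 or 1) and t be months from entry minus the follow-up time F. The mean model is

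E(Y) = b0 + b1·z + b2·t + b3·z·t,

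so b1 is the follow-up difference and b3 the slope difference.

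Assumptions: the pre visit is at month 0 for everyone, and post is at 10 weeks (2.30 months). The protocol gives two follow-up intervals after post, about 8 weeks (1.84 months) or 3 months. Hence F = 2.30 + 1.84 = 4.14 or F = 2.30 + 3 = 5.30.

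With the pre wave only, t = −F and the design has two distinct rows, [1, 0, −F, 0] and [1, 1, −F, −F], so its rank is 2 of 4. A contrast is estimable if it equals a × (first row) + c × (second row).

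- Slope difference (0, 0, 0, 1): column 2 forces c = 0 and column 1 then forces a = 0, so column 4 is 0, not 1. Not estimable.
- Follow-up difference (0, 1, 0, 0): c = 1 and a = −1 give −F in column 4, not 0. Not estimable.
- b0 needs a = 1, c = 0, which leaves −F in column 3. b2 needs a = c = 0, which leaves 0 in column 3. Neither is estimable, so 0 of the 4 coefficients can be estimated individually.
- Baseline control mean b0 − F·b2 (a = 1, c = 0) and baseline group difference b1 − F·b3 (a = −1, c = 1): both estimable.

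The result holds for any F other than 0, so it is the same for both follow-up times.

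**4. Two and three waves.** The planned model has 4 variance parameters: intercept variance, slope variance, their covariance and the residual variance. With k common occasions the data supply k(k + 1)/2 covariance moments.

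| SRS waves | Rank of mean model | Moments | Variance parameters | Position |
|---|---|---|---|---|
| Pre | 2 of 4 | 1 | 4 | neither tested contrast estimable |
| Pre, post | 4 of 4 | 3 | 4 | mean contrasts estimable; planned random-effects structure not identified without restrictions |
| Pre, post, follow-up | 4 of 4 | 6 | 4 | planned model identified |

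In the two-wave case the follow-up difference is pure extrapolation: the baseline difference plus F/2.30 times the pre-to-post change in the difference. That multiplier is 4.14/2.30 = 1.80 or 5.30/2.30 = 2.30.

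**5. Mediation and FIML.** With one SRS occasion per participant, an individual's SRS slope cannot be separated from the SRS level, so the path from memory slope to SRS slope is not identified. FIML uses the observed relation between earlier and later values. If no participant in either arm has a later value, there is no such relation to use.

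**The case against.** The strongest reply is that the lists are poor evidence of what is collected. They are addressed to parents and name no teacher form. Yet the same-rater rule in the Follow-Up section expects the same teachers at pre and post, and the only instruments marked for teachers are the ABAS and the SRS-2. In addition, the sub-heading restricting items to Visit 1 comes after the Survey Kit, which may imply that the kit itself is reused at later visits. The protocol reads as an operations manual and the SAP is an extract from a grant, so a fuller schedule of measures could exist elsewhere.

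Part of this stands. It is good reason not to conclude that the SRS-2 was omitted in practice. It does not reconcile the documents. The rule names no instrument, could refer to the ABAS alone, does not explain the missing parent SRS-2, and covers pre and post but not follow-up. The consent forms in the kit point to baseline use, and the later visits have lists of their own.

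Three narrower points are fair. First, if the rule does imply a post SRS-2, the case is two waves rather than one, and the loss is smaller (step 4). Second, the rank result assumes a common baseline time. If entry-to-baseline intervals vary, a slope might be fitted arithmetically, but it would compare different children and would not measure change within a child. Third, the end-point sentence of Hyp 2.1 speaks of prosocial behaviour without naming an instrument. Applying it to the SRS is an inference from the model paragraph, though a natural one.

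**Conclusion.** The concern holds as an inconsistency between the two documents, and it should be fixed. That the SRS-2 is not named after baseline is certain from the text. The loss of the analyses is conditional on sites following the lists as written. In that case 1 of 3 SRS waves exists, the design has rank 2 of 4, and neither SRS contrast nor the SRS mediation path can be estimated. If a post form was collected but no follow-up form, the mean contrasts could be estimated only by extrapolating to follow-up, and the planned random intercept and slope model would need added restrictions. The planned SRS analysis needs all three waves.

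The damage is bounded. Memory for faces, which the SAP's power section calls the primary dependent variable, is unaffected. So are ERP, the CASS part of Hyp 2.1 and the CASS mediation path.

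**What to change.** 1. Establish, by site and cohort, whether the SRS-2 was collected at post and at follow-up, and from which informant.
2. If it was, or still can be, add the SRS-2 to the Post-Assessment and Follow-Up lists in the informant version to be analysed. It would help to name that informant in the SAP, which does not say whether the parent or the teacher rating is the outcome.
3. If it was not collected after baseline, record in a dated amendment that the SRS parts of Hyp 2.1 and Hyp 2.2 were planned but cannot be tested, and say so in the report. The outcome should not simply be deleted. If only one later wave exists, state which model will be fitted and that any follow-up value is extrapolated.

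The cost is wording in two lists and one SAP line, plus one extra form at each later visit. Repeated teacher contact is needed only if teacher ratings are analysed. Visits already completed without the form cannot be recovered by changing a list; for those, the cost is the amendment and the disclosure.

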INVESTIGATING SOCIAL COMPETENCE IN YOUTH WITH AUTISM: A MULTISITE RCT

PROTOCOL

(CTL+click to jump to section)

CONTENTS

Investigating Social Competence in Youth with Autism: A Multisite RCT	1
Research Components of SENSE Theatre	3
Recruitment	3
EVENTS	3
Recruitment Resources	3
Maintaining Recruitment	3
Recruitment materials	3
INCLUSION/EXCLUSION CRITERIA	4
Scheduling Participants	9
Important Points to make	9
Visit Scheduling	10
Survey Kit	11
Assessment Visit	12
Setup & Consenting	12
Testing	13
Contextual Assessment of Social Skills (CASS)	13
Post-Visits	14
Post-Assessment	14
Testing	14
Post-ERP	14
Post-CASS	15
Follow-Up	15
Forms	15
Follow- Up ERP	15
Follow- Up CASS	16
SENSE Theatre/Tackling Teenage Training Intervention preparation	16
Group Assignment	16
Peers/counselors	16
Training	16
Speakers	16
Binders	16
Food	17
Room	17
Intervention	17

Daily Tasks: -----	17
Online Videos -----	18
Ordering -----	18
Constant Contact (Performance Invites)-----	18
Participant, counselor, and peer certificates-----	18
Post-Intervention -----	19
Sharing contact Info-----	19
National Database for Autism Research (NDAR)-----	20
first steps-----	20
NDAR Data structures/Templates-----	20
NDAR GUIDs-----	20
submitting data to ndar: data validation tool-----	21
NDAR Contacts -----	22
Important Notes about ndar-----	22

RESEARCH COMPONENTS OF SENSE THEATRE

- **Pre Intervention:**
 - **Assessment Visit- research site offices (2-3 hours)**
 - **ERP (45 minutes)**
 - **Contextual Assessment of Social Skills – research site offices (30 minutes)**
- **Intervention (10 week theatre program or 10 week Tackling Teenage Training program)**
- **Post Intervention:**
 - **Assessment Visit (1 hour)**
 - **ERP (45 minutes)**
 - **Contextual Assessment of Social Skills (30 minutes)**
- **Follow-up (3 months after post visit)**
 - **Assessment Visit (1 hour)**
 - **ERP (45 minutes)**
 - **Contextual Assessment of Social Skills (30 minutes)**

RECRUITMENT

EVENTS

- Regional autism community outreach groups (i.e. [Autism Tennessee](#) Conference)
- State Autism Speaks Walk
- Find other events, possible sources of recruitment using regional support groups and awareness programs (i.e. [Tennessee Disability Pathfinder website](#))

To Bring:

- SENSE Theatre mugs, stress balls, flyers, brochures, t-shirts, DVDs, SENSE banner, containers for giveaway items, pens.

RECRUITMENT RESOURCES

- Research Site Website: Coordinate Links and Information with PI and site information technology department

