***Follow-Up forms sent to both Experimental and Control groups approximately 8 weeks after post-visits.**

FOLLOW- UP ERP

- Protocol for ERP does not change in follow-up visit.
- ERP may come before Assessment during follow-up

FOLLOW- UP CASS

- Utilize research helpers unknown to participant (not the same research helpers as in the pre and post- CASS)

SENSE THEATRE/TACKLING TEENAGE TRAINING INTERVENTION PREPARATION

GROUP ASSIGNMENT

- Once randomization into SENSE Theatre or TTT is complete and participants have been assigned to groups, send letters to families informing them of what group they are assigned.
- Send out RedCap survey which collects information regarding Medication (see if there have been any changes), food allergies, behavioral information, t-shirt size.
- Add participant and research helper contacts to a designated lab cell phone

PEERS/COUNSELORS

- **Application:** Interested peers and counselors will complete an application
- **Decisions:** Lead site investigator, and theatre director will narrow down who is to be interviewed for a peer and counselor position.
- **Background checks:** all adults participating in the intervention (18 years +) must have an existing background check with Vanderbilt or go through the process of getting one.
- **Protection of Minors Training:** Make sure all counselors and peers are compliant with the site's requirements for protections of minors training. Contact site IRB for "Research Involving Minors" for more information pertinent to site requirements.
- **Consent and Video Release Forms:** sent to peers/counselors participating in intervention.
- **Intervention Information:** Send training schedule, location map, and first days schedule (via email), and an email reminder 1 week before training begins.

TRAINING

SPEAKERS

- Site PI will be responsible for contacting and choosing speakers.
- Coordinate who will be presenting when, 6 weeks before intervention begins.
 - Research Assistant/Coordinator—"Introduction to Autism"
 - Confidentiality & Code of Conduct, SENSE Theatre Manual, SENSE Lab & Theatre, Behavioral Strategies.
- Copies of past presentations can be provided to any sites by the SENSE Research Coordinator.

BINDERS

- Binder Materials:
 - Binder Covers (Color)
 - Binder spine labels (color)

- Divider Tab Labels
- Presentations (Black and White)
- Schedule
- Music/Lyrics (SENSE Theatre Intervention only)
- Name Tags
- Pre/Post Test
- SENSE Theatre Manual (Black and White)

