- Script (Black and White) (SENSE Theatre Intervention only)
- The lead site investigator, theatre director, research assistant/coordinator, and nurse(s) should be provided a sheet that details participant contact information, allergies, and medications, along with a picture for identification purposes.

FOOD

- Create catering order 3-5 days in advance
 - A light breakfast, coffee and bagels
 - Lunch based on preference (sandwiches, pizza, salads, etc.)

ROOM

- Reserve Room 2-4 weeks in advance.
- Coordinate room reservations with administration. Classrooms with projectors and whiteboard are best, conference rooms if the group is small.

INTERVENTION

Intervention Packets: before Intervention begins the following should be sent to participants 1 month before it begins.

- Letter to Parents
- Schedule with important dates
- Release Forms
- First Day Schedule
- Intervention checklist

DAILY TASKS:

- **Daily Schedule:** coordinate with lead site investigator and theatre/training director after each day of intervention program to determine schedule for next session.
- **Daily Email:** [name] will send first and last email to parents, peers, and counselors.
 - Each day, you will give a brief review of the day; give any reminders, updates, etc. Also attach schedule for next session.
- Prepare Snacks/Waters for participants/counselors/peers.
- Bring extra copies of schedule for Dry Erase Board and any participants that need a hard copy.
- Check attendance, call families who may be running late, etc.

ONLINE VIDEOS

[figure not shown]
- Contact site information technology regarding uploading peer modeling videos to a password protected website for families to access at home.

ORDERING

- Snacks
 - Lay's Chips, Gold Fish, Fruit Snacks, Water, Granola Bars
- T-Shirts:
 - Lead site investigator and site graphics design will coordinate on t-shirt design and ordering.
- Binders:
 - 1 ½" for peers/counselors
 - 1/2" for participants
 - Dividers for peer and participant binders
- Any Props/Equipment used for the production
 - Past examples include stress balls, Bradfield Lighting, etc.
 - Costumes
 - Usually provided by theatre team and participants
 - Theatre director will set up a time for costumes to be coordinated
 - Prepare a document that states:
 - What participant is wearing from site
 - What items they need to bring from home to complete costume.

CONSTANT CONTACT (PERFOMANCE INVITES)

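### The straight-line intercept equals the true follow-up difference only if the gap keeps growing after treatment ends, and the three-month span used to justify it is at least 5.3 months by the Protocol's schedule

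*SAP*

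**What the plan says.** In the SAP (3.C.12, Statistical Analysis under Specific Aim 1), treatment enters a two-level growth model by "predicting random intercepts and random linear slopes", with time in months and three occasions: pre, post and follow-up. On the origin of time it says: "Time will be centered at follow-up to enable interpreting the intercept as an end-point estimate". The EXP-ACC difference in that intercept is then tested. It is the only planned test of the second half of Hyp 1.1, "EXP youth will also have higher levels of memory for faces at follow-up", and of the matching claim for prosocial behavior in Hyp 2.1.

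Linearity is defended thus: "linear model is a reasonable model of social growth for such a short period (i.e., three months) with people who have a social impairment". No visit-specific contrast and no check of linearity is planned.

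The Protocol bears on the time axis in three places:
- Research Components: "Intervention (10 week theatre program or 10 week Tackling Teenage Training program" and "Follow-up (3 months after post visit".
- Follow-Up, Forms: "Follow-Up forms sent to both Experimental and Control groups approximately 8 weeks after post-visits".
- Intervention: packets, of which "the following should be sent to participants 1 month before it begins". This hints at some lead time between the pre visit and the first session.

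**The concern.** Three months matches only the interval from post to follow-up in Research Components, not the span that the line covers. More importantly, the line runs across the end of treatment. A straight line has two mean parameters per arm for three visits, so the fitted gap at follow-up is a weighted combination of all three observed gaps. It equals the real follow-up gap only if the EXP-ACC difference grows after treatment at the rate it grew during treatment. Only the gap has to be linear; a bend common to both arms cancels.

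If the gap stops growing or shrinks, the reported follow-up difference borrows from the post visit. At stake are the follow-up estimate, its interval and, in the extreme case, a claim of lasting benefit where none remains.

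**Working it through.** **Span.** With 4.348 weeks to a month, 10 weeks is 10/4.348 = 2.30 months. Adding 3 months gives 5.30. This is a minimum, because it assumes that the pre and post visits abut the program. An assumed one-month lead gives visits at 0, 3.3 and 6.3 months. The SAP's figure of three months is not reproduced.

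**Weights.** For t = (0, 2.3, 5.3) the mean is 2.533 and the sum of squares about it is 14.127. The fitted value at follow-up puts weight 1/3 + (5.3 - 2.533)(t - 2.533)/14.127 on each visit's gap:
- pre: -.163
- post: .288
- follow-up: .875

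For (0, 3.3, 6.3) the weights are -.166, .349 and .817. With complete data on a common schedule, generalized least squares under a random intercept, random slope and independent residual gives the same weights. The bias therefore does not depend on the covariance assumed.

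**Expected estimate.** Randomization makes the expected pre gap zero. With gap D at post and fD at follow-up, the intercept estimates (.288 + .875f)D, or (.349 + .817f)D with the lead. It is unbiased at f = 5.3/2.3 = 2.30, or 6.3/3.3 = 1.91. (It is also unbiased, trivially, if there is no gap at either visit.)

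| Course after post | Truth | Estimate, 5.3 months | Estimate, 6.3 months |
|---|---|---|---|
| Gap holds (f = 1) | D | 1.16D | 1.17D |
| Gap halves (f = .5) | .5D | .73D | .76D |
| Gap vanishes (f = 0) | 0 | .29D | .35D |

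**Rejection rates under complete fade.** Assumptions:
- 108 per arm (216/2; no allocation ratio is stated)
- two-sided 5%, complete data, no cohort effect
- baseline SD 1, intercept variance r and residual variance 1 - r, with r from .1 to .7
- slope variance expressed as s, the between-child variance of true change over the span: s = .25 or .5 (SD .5 or .71), uncorrelated with the intercept

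The squared weights sum to the last weight, so the intercept's variance per child is V = r + .875(1 - r) + s, and SE = sqrt(2V/108).

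Example with r = .5, s = .25, D = .5: V = .5 + .4375 + .25 = 1.188 and SE = .148. The bias is .288 x .5 = .144, which is .97 SE. The rejection rate is about 16%, and coverage of the true gap (zero) is about 84%. In the same setting, coverage is about 88% if the gap halves (bias .113) and 91-92% if it holds (bias .081).

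| D = .5, complete fade | 5.3 months | 6.3 months |
|---|---|---|
| With random slopes (s = .25 or .5) | 14-17% | 19-23% |
| Without slope variance (s = 0) | 19-20% | 26-29% |

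At D = .25 the rate is about 7-11% over all these cases.

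**Price of a visit-specific contrast.** Its variance per child is 1 + s and its weights are (0, 0, 1). Relative to V:
- 5.3 months, r = .7, s = .5: 1.5/1.463 = 1.03
- 5.3 months, r = .1, s = 0: 1/.888 = 1.13
- 6.3 months, r = .1, s = 0: 1/.835 = 1.20

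**The case against.** The strongest reply is that linearity is an openly stated assumption and that nothing in the documents says benefit fades. That stands. If the gap holds, the claim that EXP is higher at follow-up is true and only its size is overstated. If the gap halves, a follow-up effect still exists, so a significant result is not false. Only near-total fade gives a wrong qualitative conclusion. Nor does the longer span break linearity by itself; a change of course off treatment would.

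Several stronger readings are tempting, but the documents do not support them:
- **A span of about 4.1 months and an unbiased ratio near 1.8**, taken from the 8-week figure. That sentence concerns when follow-up forms are sent. The face-memory tasks, ERP and CASS belong to the follow-up visit, and the SRS-2 is not on the Protocol's list of follow-up forms. The 8 weeks therefore attaches to none of the Hyp 1.1 or 2.1 outcomes listed at follow-up.
- **A fixed requirement of f = 2.30.** This is the maximum on the Research Components timing. Any lead or lag around the program lowers it.
- **A false-positive rate of 20-30%.** Those figures leave out the random slopes that the SAP specifies, and they need D = .5 with complete fade. The SAP's .5 is the effect anticipated for the efficacy tests, not a post gap that disappears.
- **A faulty slope test or mediation model.** The hypotheses ask about growth and follow-up level, and the slope test addresses growth. A missed pre-to-post effect would answer a question they do not pose.

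With no effect at any visit, the intercept test keeps its 5% error.

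**Conclusion.** The concern holds in a limited form. The stated three months is wrong for the modelled span, which is at least 5.3 months on the Research Components timing. The intercept is not a free-standing follow-up difference: it is too high for any follow-up gap smaller than 2.30 times the post gap (1.91 with a one-month lead, less with more slack), and that includes a gap that is fully maintained.

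The algebra is firm, given a zero expected gap at pre and complete data on a common schedule. With missing data under FIML or varying visit times the weights change, but the need for a linear gap does not. The practical harm is uncertain because f is unknown. It ranges from an estimate about 16% too high with somewhat low coverage, to a rejection rate of about 14-23% with random slopes at D = .5 if the gap vanishes. The error rates, unlike the bias, rest on the assumed variances, equal arms and the absence of cohort effects.

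**What to change.** 1. In the SAP, replace the three-month figure with the actual span from pre to follow-up. Reconcile the 3-month follow-up visit in the Protocol's Research Components section with the 8-week mailing of forms in its Follow-Up section, so that one time axis is defined.
2. Base the follow-up-level claims of Hyp 1.1 and 2.1 on the EXP-ACC contrast at follow-up, from a model with categorical visit and unstructured covariance, using FIML and the same cohort correction. Keep the linear slope test for the growth claims, and keep the mediation model for Hyp 2.2 as planned.

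This needs no new data or visits. The price is about 3-13% more variance than the linear intercept at 5.3 months, and up to 20% with a one-month lead. If growth is truly linear, then at 5.3 months without slope variance power goes from 96-97% to 96% for a follow-up gap of .5, and from 46-50% to 45% for a gap of .25.

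A pre-to-post contrast and a mediation analysis on change scores could be added as supporting analyses, but the correction does not require them.
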